### 2.3.1 Adverse event profile

In general, in EP0069, there were no new or unexpected safety signals. The most frequently reported treatment-emergent adverse events (TEAEs) for subjects overall were somnolence, dizziness, headache, fatigue, and irritability. Overall, the most frequently reported TEAEs considered drug-related by the Investigator were somnolence, dizziness, and fatigue. Four serious TEAEs were reported for 2 subjects (1 subject had a serious TEAE of status epilepticus and 1 subject had serious TEAEs of impaired judgment, delirium, and dysphoria) during the On-PSL Overall Period. There were no deaths reported during the study. During the On-PSL Overall Period, in the 18 subjects who reported TEAEs leading to a dose reduction of PSL, the most common TEAEs were dizziness, somnolence, and fatigue. One subject withdrew from the study due to TEAEs of dysphoria and mood swings. There was no evidence for any consistent effect on laboratory parameters, vital signs, weight, ECG evaluations, physical examinations, or neurological examinations in the overall population. Based on the study results, treatment with PSL was generally well tolerated, with an acceptable tolerability and safety profile pointing to an overall positive benefit/risk balance.

No subjects have completed the OLE study (EP0073). As of June 2018, 18 subjects (42.9%) had discontinued.

In summary, in the Phase 1 program 181 healthy subjects and 20 patients with epilepsy (male and female) have been exposed to PSL at single doses up to 490mg (58 healthy volunteers) and repeated doses up to 400mg bid for up to 12 days (123 healthy subjects and 20 patients) in completed studies. In the Phase 2 proof of concept study (EP0069), 55 subjects were exposed at

doses up to 400mg bid during the maintenance phase of the study. A total of 42 of the 55 subjects enrolled in the OLE study, during which they were allowed to adjust their PSL dose.

The safety findings to date suggest that the AEs experienced by subjects receiving single and repeated doses of PSL are limited principally to central nervous system (CNS) effects and that these are consistent with the known pharmacology of PSL, ie, similar to AEs associated with other SV2A- and GABA-A-targeting AEDs. The AEs tend to be dose-related in frequency and intensity, self-limiting, and tend to decrease in intensity over the first few days of dosing.

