- m AED samples will ideally be taken immediately prior to dose of concomitant medication on each occasion. If this is not possible, then the sample may be taken at any time after dose and the timing of sample in relation to dose should be kept the same ( $\pm 1$  hour) on each occasion for each subject. Therefore, the timing of visits for each subject when AED samples are collected should be scheduled approximately at the same time whenever possible. Assay of parent PSL and metabolites may be included in the AED panel of tests at Visits 6 and 7.
- n On Visits 6 and 7, unless the concomitant AED sample is within  $\pm 5$  minutes of a scheduled MITRA® sample for PSL assay, a separate, additional MITRA sample will be taken at same time as the concomitant AED blood sample.
- o Subjects are requested to provide blood samples for measurement of PSL PK whenever possible. On Visits 3, 5, and 6, site personnel should obtain blood samples, via MITRA microsampling, for measurement of random PSL levels at any time between IMP intakes and record accurately the time of last IMP intake and the time of sample collection. On Visits 4 and 7, blood samples, via MITRA microsampling, for measurement of sparse PK profiles will be collected as follows: immediately before IMP intake (maximum 15 minute before intake) and then 3 times after (between 30 minutes and 3 hours after IMP intake), taken at least 30 minutes apart. All samples may be taken either at home or in the site or partly at home and partly at the site.
- p For all female subjects, serum pregnancy test at Visits 1 and 7 (in case the subject enters into the OLE study) and where applicable. Urine pregnancy test will be used at other visits for female subjects of childbearing potential.
- q Seizure counts are collected on the subject's daily record card on a daily basis.
- r At each visit following an IMP dispensation, IMP should be presented to check for compliance.
- s Study termination will occur at Visit 8 only for subjects enrolling in OLE study, EP0093. The SFU Visit will be performed only for subjects who do not enter the OLE study, EP0093.

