### 11.1.2.2 Rule for repetition of an adverse event

An increase in the intensity of an AE should lead to the repetition of the AE being reported with:

- The outcome date of the first AE that is not related to the natural course of the disease being the same as the start date of the repeated AE, and the outcome of "worsening"
- The AE verbatim term being the same for the first and repeated AE, so that the repeated AE can be easily identified as the worsening of the first one

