10.2 Adverse events

Adverse events are recorded on the AE CRF as they occur, from the time informed consent is granted until study completion or study termination (end of the SFU period 30 days after the last IMP intake). All AEs will be coded using the latest available version of MedDRA.

A treatment-emergent adverse event (TEAE) is defined as any event not present prior to the initiation of the first dose of study treatment or any unresolved event already present before initiation of the first dose that worsens in intensity following exposure to the treatment. The number and percentage of subjects who experience TEAEs at any time during the study will be summarized by SOC and PT. The following tabular summaries will be presented for the SS:

- Incidence of TEAEs during the Treatment Period – Overview. Of note, the corresponding table is required for data transparency reporting.
- Incidence of TEAEs by period (Treatment Period, Titration and Stabilization Period, Maintenance Period, Conversion Period, and Taper and SFU Period)
- Incidence of Serious TEAEs by period (Treatment Period, Titration and Stabilization Period, and Maintenance Period)
- Incidence of TEAEs leading to discontinuation by period (Treatment Period, Titration and Stabilization Period, and Maintenance Period)
- Incidence of TEAEs leading to dose reduction during the Stabilization Period

The following will be presented for TEAEs during the overall Treatment Period:

- Subject numbers for TEAEs
- Incidence of TEAEs occurring in at least 5% of subjects in any treatment group
- Incidence of TEAEs occurring in at least 2% of subjects in any PSL group and greater than placebo group
- Incidence of TEAEs by Relationship
- Incidence of TEAEs by Maximum Intensity
- Incidence of SAEs by Relationship. Of note, the corresponding table is required for data transparency reporting.
- Incidence of Fatal TEAEs by Relationship. Of note, the corresponding table is required for data transparency reporting.

- Incidence of Non-Serious TEAEs above the threshold of 5% of subjects in any treatment group. Of note, the corresponding table is required for data transparency reporting.
- Summary of the duration in days per event for the following TEAEs: somnolence, dizziness, fatigue, irritability and headache. In this analysis, if an AE is ongoing, the duration will be calculated till the date of final contact.

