Summaries will be presented based on standard Sponsor AE table formats and considering formats used for the PSL program.

Where dates are missing or partially missing, AEs will be assumed to be treatment-emergent, unless there is unmistakable evidence (through comparison of partial dates, see Section 4.2) to suggest that the AE started prior to the first dose of study treatment. Summary tables will contain counts of subjects, percentages of subjects in parentheses and the number of events where applicable. A subject who has multiple events in the same MedDRA category (SOC or PT) will be counted only once in the subject count for that category, however all events will be included in the event count for the category. In summaries including relationship to study treatment, the following relationships will be summarized: 'Not related', 'Related'. A subject may be counted more than once according to the relationship to study treatment. Events with missing relationship will be considered as 'Related' to the last given study product for summary purposes but recorded as missing in the listings. In summaries of the maximum intensity, the following intensity categories will be summarized: 'Mild', 'Moderate', 'Severe'. Subjects who experience the same event multiple times, with differing severities, will be included in the most severe category. Events with missing intensity will be considered as 'Severe' events for summary purposes but recorded as missing in the listings. The main reasons for treatment discontinuation will be listed by subject. The daily dose of study medication corresponding to the AE onset date will be included in the listing. Daily dose will be derived from 'Study Medication Administration' CRF.

Adverse event summaries will be ordered in terms of decreasing frequency for SOC, and PT within SOC, within the PSL total group column.

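### The planned summary of adverse event duration counts ongoing events as finished at last contact and has no rule for joining records split by a worsening, so mean duration is understated and resolution cannot be read from it

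*SAP*

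**What the plan says.** Among the summaries introduced by "The following will be presented for TEAEs during the overall Treatment Period", SAP 10.2 lists one on duration: "Summary of the duration in days per event for the following TEAEs: somnolence, dizziness, fatigue, irritability and headache". For events with no end, it adds: "In this analysis, if an AE is ongoing, the duration will be calculated till the date of final contact". It mentions no censoring and no separate count of resolved and ongoing events. SAP 3.1 makes the default statistics for a continuous variable n, mean, SD, median, minimum and maximum. SAP 10 has safety data shown for each arm and for the padsevonil (PSL) arms combined.

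Protocol 11.1.2.2 governs how a worsening is recorded: "An increase in the intensity of an AE should lead to the repetition of the AE being reported with" two features. The closing date of the first record is set as "being the same as the start date of the repeated AE", with an outcome of worsening, and both records carry the same verbatim term. On several records of one term in one subject, SAP 10.2 counts the subject once, "however all events will be included in the event count for the category". It does not say whether contiguous records are joined for the duration summary.

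Final contact depends on the subject's route. According to the notes to protocol Table 5-1, "Study termination will occur at Visit 8 only for subjects enrolling in OLE study, EP0093", which is nominally Day 133. Other completers are seen at the Safety Follow-Up Visit, nominally Day 161.

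**The concern.** A table of event durations is read as an answer to how long these effects last. Under the SAP rule, an event that resolved on Day 133 and one still present on Day 133 produce the same number, so the table cannot separate recovery from the end of observation. The longest events lose the most time. Splitting works in the same direction: an episode that became more severe contributes two shorter durations instead of one long one.

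Safety and tolerability form the secondary objective, and the five terms are the ones protocol 2.3.1 names as the most frequent in the proof-of-concept study. This is the only summary of event duration in the SAP.

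Comparison between arms could also suffer. Final contact falls at different times by route. Titration steps differ by arm (protocol Table 7-1), so worsening, and hence splitting, could differ too. Placebo subjects entering the extension start PSL in the Conversion Period (protocol 5.1), so a placebo-arm event still open at Visit 7 accrues time on active drug before its cut-off at Visit 8.

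**Working it through.** The documents give no figure for event duration, for the share of events ongoing, or for the frequency of worsening, so there is no planned figure to reproduce. What follows is an illustration of direction and range.

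**Inputs from the documents.** Treatment Period events have onset from Day 1 to Day 112 (Visit 7). Final contact is Day 133 for extension entrants and Day 161 for other completers. An onset on Day 112 therefore leaves 133 − 112 = 21 days of follow-up for the first group and 161 − 112 = 49 for the second.

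**Assumptions, not from the documents.** Exponential durations with true mean m of 7 to 120 days; onset uniform over Days 1–28 or Days 1–112; one scenario with contact lost 30 days after onset; 10% to 50% of episodes worsening once.

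**Truncation.** With follow-up C after onset, the recorded mean is m(1 − e^(−C/m)), so the proportional shortfall is e^(−C/m) averaged over C. For C uniform between a and b it is m/(b − a) × (e^(−a/m) − e^(−b/m)).

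Example with m = 60, onset Days 1–112 and contact on Day 133, so C runs from 21 to 132: 60/111 × (e^(−0.35) − e^(−2.2)) = 0.5405 × (0.7047 − 0.1108) = 0.32.

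Shortfall of the recorded mean:

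| True mean (days) | Onset 1–28, contact Day 133 | Onset 1–28, contact Day 161 | Onset 1–112, contact Day 133 | Contact lost 30 days after onset |
|---|---|---|---|---|
| 7 | 0% | 0% | 0% | 1% |
| 14 | 0% | 0% | 3% | 12% |
| 30 | 2% | 1% | 13% | 37% |
| 60 | 14% | 9% | 32% | 61% |
| 120 | 37% | 30% | 55% | 78% |

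A simulation of 200,000 events per scenario gave the same percentages. It also showed that the uncorrected median is right in most cells. At contact Day 133 with onset over Days 1–112 it falls from 41.6 to 34.0 days (m = 60) and from 83.3 to 48.6 days (m = 120). The Kaplan-Meier median recovers 41.6 and 83.1 there. With contact lost at 30 days and m of 60 or more, the Kaplan-Meier median is not reached.

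**Splitting.** If a share w of episodes worsens once, total time is unchanged but is divided among (1 + w) records per episode. The per-record mean is 1/(1 + w) of the per-episode mean:

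- w = 10%: 0.91, so 9% low
- w = 25%: 0.80, so 20% low
- w = 50%: 0.67, so 33% low

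The median moves too. For a 30-day mean, with the worsening at a random point in the episode, it falls from 20.8 to 17.9, 14.7 and 11.3 days.

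**Both together**, with onset Days 1–28, contact on Day 133 and w = 25%: for m = 60, (1 − 0.14) × 0.80 = 0.69, so 31% low; for m = 120, (1 − 0.37) × 0.80 = 0.50, so 50% low. For m = 14 truncation is nil and the whole 20% comes from splitting.

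**The case against.** The case for leaving the table alone has substance. It is one descriptive line with no hypothesis attached, in a study whose analyses were cut back after early termination. The default statistics include the median, which truncation often leaves unchanged, and for short events starting in titration even the mean is hardly affected. Protocol 11.1.3 asks that an ongoing event be followed to resolution or a stable state where possible, which reduces the number left open. The imputation rules in SAP 4.2.2 place a partial stop date at the end of the month and often a partial start date at its beginning, which can lengthen durations. All of this stands, and it limits the size of the problem. It does not remove the defect: an unresolved event still counts as a completed one, and splitting moves the median as well as the mean.

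Four stronger readings are tempting and are not supported.

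- *The SAP chooses to count each worsening as a new event.* It says nothing about worsenings. The effect follows from the protocol's recording rule plus the SAP's silence. The protocol keeps the verbatim term identical so that a repeat can be recognised, so a programmer could link the records; nothing instructs it.
- *The table is meant to support a claim that these events pass by themselves.* Protocol 2.3.1 does say "The AEs tend to be dose-related in frequency and intensity, self-limiting, and tend to decrease in intensity over the first few days of dosing", but as a summary of earlier PSL data. Neither document ties the present table to it.
- *Durations are cut to a fraction of their true length.* Dramatic examples can be built: a 60-day true mean with 28 days of follow-up gives 60 × (1 − e^(−28/60)) = 22.4 days. For an extension entrant that needs onset at Day 133 − 28 = Day 105, and the 60-day mean has no source in the documents.
- *The arms are biased by different amounts.* This holds only if they differ in worsening, drop-out or extension entry, and no figures are given.

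**Conclusion.** The point holds at low severity. As written, SAP 10.2 treats right-censored durations as complete and does not show how many events are ongoing. Together with protocol 11.1.2.2 it leaves continuous episodes split at each worsening. Each effect lowers mean duration, and the table cannot show resolution.

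The size cannot be determined from the documents. Under the stated assumptions, truncation at Day 133 lowers the mean by about 0% to 55%, depending on true duration and time of onset, and by more with early loss of contact. Splitting lowers it by 9% to 33%. Partial-date imputation may offset some of this. For short events starting in titration, truncation is negligible and splitting is the main effect. No efficacy or safety test is touched.

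**What to change.** In SAP 10.2, replace the duration line with a time-to-resolution summary:

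- Link contiguous records of the same subject and term, where the earlier record has an outcome of worsening, into one episode before any duration is computed.
- Report by arm the numbers of episodes resolved and ongoing.
- Give the Kaplan-Meier median with 25th and 75th percentiles, censoring ongoing episodes at final contact.
- For subjects entering the Conversion Period, censor at Visit 7, or show this as a second version, because placebo subjects then start PSL.

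The cost is a wording change and one somewhat more complex descriptive table in place of the present one; no new data are needed. There are three drawbacks. Some percentiles may not be reached. Censoring at Visit 7 leaves little follow-up for late-onset events. A subject can contribute more than one episode, so the number of subjects should stand beside the number of episodes, and the percentiles should be read as descriptive only.

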10.3 Clinical laboratory evaluations

Clinical laboratory hematology, chemistry and urinalysis measurements obtained from blood/urine samples collected throughout the study are presented in Table 10-1.

During the study, non-protocol-specified lab parameters (unplanned) may be collected. Summaries of lab parameters will only include planned parameters as specified in the protocol. All lab parameter values will be listed and summarized using international units.

The observed value and change from Baseline will be summarized descriptively by treatment group and PSL total group and scheduled study visit. The Last Visit, minimum, and maximum post-baseline values during the Treatment Period will also be included. These summaries will be organized by lab function panel and parameter.

Shift from Baseline to the maximum and minimal values during the Treatment Period based on normal range (Low, Normal, High) will be provided for hematology and blood chemistry parameters in Table 10-1.

Possibly clinically significant treatment-emergent (PCST) criteria have been developed based on FDA Division of Neuropharmacologic Drug Products guidelines with some UCB-defined additions and are provided in Appendix 13.1. For lab parameters with PCST criteria, the number and percentage of subjects with a PCST value at any time (scheduled and unscheduled visits) during the Treatment Period will be summarized by treatment group and PSL total group. . Treatment-emergent values are those occurring any time on or after the first dose of study medication in EP0092. Subject numbers for those meeting the PCST criteria will also be presented.

Table 10–1: Laboratory measurements

Hematology	Chemistry	Urinalysis
Basophils	ALP	Glucose
Eosinophils	ALT	pH
Hematocrit	AST	RBC
Hemoglobin	Bilirubin	Total protein
Lymphocytes	BUN or urea	WBC
MCH	Calcium	Microscopy (WBC, RBC, casts, crystals, bacteria) ^a
MCHC	Chloride	Other
MCV	Creatinine	FSH ^b
Monocytes	Glucose	
Neutrophils	HDL	
Platelet count	LDH	
RBC count	LDL	
WBC count	Magnesium	
	Potassium	
	Sodium	
	Total bilirubin	
	Total cholesterol	

ALP=alkaline phosphatase; ALT=alanine aminotransferase; AST=aspartate aminotransferase; BUN=blood urea nitrogen; HDL=high density lipoprotein; FSH=follicle stimulating hormone; LDH=lactate dehydrogenase; LDL=low density lipoprotein; MCH=mean corpuscular hemoglobin; MCHC=mean corpuscular hemoglobin concentration; MCV=mean corpuscular volume; RBC=red blood cell; WBC=white blood cell

^a Microscopy will be performed only in case of abnormalities.

^b Only applicable to postmenopausal women

10.3.1 Subjects with potential drug-induced liver injury (PDILI)

There are specific criteria described in the protocol Section 11 to evaluate subjects for potential drug-induced liver injury (PDILI). The evaluations required by protocol for PDILI subjects are collected on the following CRFs:

- Most Recent Study Medication Administration, for PDILI
- Laboratory Tests DILI
- Vital Signs DILI
- Hepatic Event Supplemental Medical History for PDILI

- Potential Hepato-Toxic Medications Inquiry for PDILI
- Symptoms of Hepatitis and Hypersensitivity for PDILI
- Lifestyle PDILI
- Family Medical History for PDILI

Listings will be prepared presenting subjects with PDILI data. A summary of number and percent of subjects meeting PDILI criteria (ALT, AST, total bilirubin, ALP, and presence of symptoms) during the Treatment Period (scheduled and unscheduled visits) will be provided following the UCB standard table shell for PDILI Data. Subjects who met these criteria will be listed.

ALT Criteria	AST Criteria	Total Bilirubin Criteria	ALP Criteria	Presence of Symptoms
≥3xULN	≥3xULN	≥2xULN	≥2xULN	NA
≥8xULN	≥8xULN	NA		NA
≥3xULN	≥3xULN	NA		Y
≥3xULN <5xULN and ≥2x Baseline	≥3xULN <5xULN and ≥2xBaseline	<2xULN		N
≥5xULN <8xULN and ≥2x Baseline	≥5xULN <8xULN and ≥2xBaseline	<2xULN		N
≥5xULN and ≥2xBaseline	≥5xULN and ≥2xBaseline	<2xULN		N

N=No; NA=Not Applicable; ULN= upper limit of normal; Y=Yes.

A summary table highlighting the potential cases of Hy's Law, within each treatment group will be presented.

Potential Hy's Law, is defined as ≥3xULN ALT or AST with coexisting ≥2xULN total bilirubin in the absence of ≥2xULN ALP, with no alternative explanation for the biochemical abnormality.

In order to meet the above criteria, a subject must experience the elevation in bilirubin and ALT or AST at the same visit. For example, a subject who experiences a ≥2 x ULN elevation of bilirubin at one visit and a 3 x ULN elevation in ALT (or AST) at a subsequent visit has not fulfilled the Hy's law criteria.

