### **6.3.1 Potential drug-induced liver injury IMP discontinuation criteria**

Subjects with potential drug-induced liver injury (PDILI) must be assessed to determine if IMP must be discontinued. In addition, all concomitant medications and herbal supplements that are not medically necessary should be discontinued.

The PDILI criteria below require immediate and permanent discontinuation of IMP:

- Subjects with either of the following:
  - ALT or AST  $\geq 5\text{x ULN}$
  - ALT or AST  $\geq 3\text{xULN}$  and coexisting total bilirubin  $\geq 2\text{xULN}$

The PDILI criterion below requires immediate discontinuation of IMP:

- Subjects with ALT or AST  $\geq 3\text{xULN}$  who exhibit temporally associated symptoms of hepatitis or hypersensitivity. Hepatitis symptoms include fatigue, nausea, vomiting, and right upper quadrant pain or tenderness. Hypersensitivity symptoms include fever (without clear alternative cause), rash, or eosinophilia (ie,  $>5\%$ ).

If a nondrug-related cause for the symptoms can be confirmed, these subjects may resume IMP administration after discussion with the responsible UCB physician, but only when the requirements for rechallenge with IMP as provided in Section 11.6.1.2.1 are followed.

The PDILI criterion below allows for subjects to continue on IMP at the discretion of the Investigator.

- Subjects with ALT or AST  $\geq 3$ xULN (and  $\geq 2$ x baseline) and  $< 5$ xULN, total bilirubin  $< 2$ xULN, and no eosinophilia (ie,  $\leq 5\%$ ), with no fever, rash, or symptoms of hepatitis (eg, fatigue, nausea, vomiting, and right upper quadrant pain or tenderness).

Evaluation of PDILI must be initiated as described in Section 11.6.1. If subjects are unable to comply with the applicable monitoring schedule, IMP must be discontinued immediately.

Investigators should attempt to obtain information on subjects in the case of IMP discontinuation to complete the final evaluation. Subjects with PDILI should not be withdrawn from the study until investigation and monitoring are complete. All results of these evaluations and observations, as well as the reason(s) for IMP discontinuation and subject withdrawal (if applicable), must be recorded in the source documents. The eCRF must document the primary reason for IMP discontinuation.

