### 11.1.1.3 Adverse events of special interest

An AE of special interest is any AE that a regulatory authority has mandated be reported on an expedited basis, regardless of the seriousness, expectedness, or relatedness of the AE to the administration of a UCB product/compound.

Potential Hy’s Law, defined as  $\geq 3 \times \text{ULN}$  ALT or AST with coexisting  $\geq 2 \times \text{ULN}$  total bilirubin in the absence of  $\geq 2 \times \text{ULN}$  ALP, with no alternative explanation for the biochemical abnormality, must ALWAYS be reported to UCB as an AE of special interest (ie, without waiting for any additional etiologic investigations to have been concluded). Follow-up information should then be reported if an alternative etiology is identified during investigation and monitoring of the subject.

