**Table 11-3: Required investigations and follow up for PDILI**

Laboratory value			Immediate		Follow up	
ALT or AST	Total bilirubin	Symptoms a of hepatitis or hypersensitivity	Consultation requirements	Actions	Testing	Evaluation
≥3xULN	≥2xULN b	NA	Hepatology consult. c	Immediate, permanent IMP discontinuation.	Essential: Must have repeat liver chemistry values and additional testing completed ASAP (see Section 11.6.1.3); recommended to occur at the site with HCP.	Monitoring of liver chemistry values at least twice per week until values normalize, stabilize, or return to within baseline values. d
≥8xULN	NA	Medical Monitor must be notified within 24 hours (eg, by laboratory alert) and subject discussed with Medical Monitor ASAP.	Immediate, temporary or permanent, IMP discontinuation.			
≥3xULN	NA	Yes				
≥3xULN (and ≥2x baseline) and <5xULN	<2xULN	No	Discussion with Medical Monitor required if the criterion that allows for IMP continuation is met.	Further investigation and immediate IMP discontinuation not required (see Section 11.6.1.2).	Not required unless otherwise medically indicated (at discretion of Investigator).	
≥5xULN (and ≥2x baseline)	<2xULN	No	Discussion with Medical Monitor required.	Immediate, permanent IMP discontinuation.	Essential: Every attempt must be made to have repeat liver chemistry values and additional testing completed within 48 hours at the site with HCP (see Section 11.6.1.3).	Monitoring of liver chemistry values at least twice per week until values normalize, stabilize, or return to within baseline values. d

---

ALP=alkaline phosphatase; ALT=alanine aminotransferase; ASAP=as soon as possible; AST=aspartate aminotransferase; HCP=healthcare practitioner; IMP=investigational medicinal product; NA=not applicable; PDILI=potential drug-induced liver injury; ULN=upper limit of normal.

a Hepatitis symptoms include fatigue, nausea, vomiting, and right upper quadrant pain or tenderness; hypersensitivity symptoms include eosinophilia (>5%), rash, and fever (without clear alternative cause).

b If the subject also has  $\geq 2 \times$ ULN ALP, the possibility of an indication of biliary obstruction should be discussed with the Medical Monitor.

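### Row 1 of the SAP liver-injury table adds ALP ≥2xULN to a protocol stopping criterion that has no ALP condition, so no planned summary counts the subjects who meet that criterion

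*SAP*

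**What the plan says.** **Protocol 6.3.1** introduces two criteria with the words "The PDILI criteria below require immediate and permanent discontinuation of IMP". One is ALT or AST ≥5xULN. The other is ALT or AST ≥3xULN "and coexisting total bilirubin" ≥2xULN. Neither mentions ALP.

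**Protocol Table 11-3** repeats the second criterion in its first row, with the action "Immediate, permanent IMP discontinuation". The table has no ALP column. ALP appears only in footnote b, which says that if ALP is also ≥2xULN, "the possibility of an indication of biliary obstruction should be discussed with the Medical Monitor".

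**SAP 10.3.1** refers to the liver-injury criteria in protocol Section 11 and then plans "A summary of number and percent of subjects meeting PDILI criteria (ALT, AST, total bilirubin, ALP, and presence of symptoms". Its table has five columns: ALT, AST, total bilirubin, ALP and presence of symptoms. Row 1 reads "≥3xULN ≥3xULN ≥2xULN ≥2xULN NA". The ALP cell is blank in the other five rows.

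The same section plans a separate table of potential Hy's Law cases: ALT or AST ≥3xULN with total bilirubin ≥2xULN, "in the absence of ≥2xULN ALP, with no alternative explanation for the biochemical abnormality". Protocol 11.1.1.3 gives the same definition and says that such a case "must ALWAYS be reported to UCB as an AE of special interest".

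SAP 3.9, which lists departures from the protocol-defined analyses, does not mention an ALP condition.

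**The concern.** Row 1 stands where the first row of protocol Table 11-3 stands and has the same transaminase and bilirubin thresholds, but it adds a third laboratory condition. A subject who must stop study drug under protocol 6.3.1, and whose ALP is below 2xULN, does not satisfy it.

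At stake is a basic safety figure: how many subjects in each arm met this stopping criterion. A reader of the report would naturally take row 1 to be that number, when it would be only the subset with raised ALP. The listing in SAP 10.3.1 of subjects who met the table's criteria would carry over the same restriction.

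**Working it through.** The plan states no figure to reproduce, so the check is one of logic: take every kind of subject who meets the protocol criterion and see which SAP row counts that subject.

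**Inputs**

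- Protocol criterion (6.3.1; Table 11-3, first row): ALT or AST ≥3xULN and total bilirubin ≥2xULN.
- SAP rows as printed (10.3.1):
  - Row 1: ≥3xULN, bilirubin ≥2xULN, ALP ≥2xULN
  - Row 2: ≥8xULN, any bilirubin
  - Row 3: ≥3xULN with symptoms, any bilirubin
  - Row 4: 3 to <5xULN and ≥2x baseline, bilirubin <2xULN, no symptoms
  - Row 5: 5 to <8xULN and ≥2x baseline, bilirubin <2xULN, no symptoms
  - Row 6: ≥5xULN and ≥2x baseline, bilirubin <2xULN, no symptoms
- Reading: the ALT and AST columns are joined by *or*, as in the protocol, and the remaining columns by *and*. The SAP table states neither.

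**Enumeration.** With bilirubin ≥2xULN throughout, the combinations are 3 transaminase bands (3 to <5, 5 to <8, ≥8xULN) × 2 ALP levels (<2, ≥2xULN) × symptoms no/yes × at least 2x baseline no/yes = 3 × 2 × 2 × 2 = 24.

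**Row 1 as printed.** It takes the ALP ≥2xULN half: 24 / 2 = 12 of 24. The other 12 fall outside it, as follows:

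| ALT or AST (xULN) | Symptoms | Combinations | Counted in |
|---|---|---|---|
| 3 to <5 | no | 2 | no row |
| 3 to <5 | yes | 2 | row 3 |
| 5 to <8 | no | 2 | no row |
| 5 to <8 | yes | 2 | row 3 |
| ≥8 | no | 2 | row 2 |
| ≥8 | yes | 2 | rows 2 and 3 |

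Rows 2 and 3 together pick up 2 + 2 + 2 + 2 = 8. The remaining 12 − 8 = 4 are in no row, because rows 4 to 6 all require bilirubin <2xULN. Two of those four, at 5 to <8xULN, also meet the separate ≥5xULN criterion of protocol 6.3.1.

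**Row 1 without the ALP condition.** All 24 of 24 fall in row 1.

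**Does the Hy's Law table restore the count?** All 12 combinations with ALP <2xULN meet its laboratory part. Read literally, it leaves out anyone whose abnormality has another explanation. Adding row 1 to that table therefore does not recover the number meeting the protocol criterion. What no summary of either kind counts is the group with ALP <2xULN, transaminases 3 to <8xULN, no symptoms, and an alternative explanation.

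**The case against.** **Most of these subjects are counted somewhere.** This is right, and it limits the point. A reader might infer that everyone with ALP <2xULN and an alternative explanation disappears from both tables. The documents do not support that: rows 2 and 3 have no ALP condition and count those at ≥8xULN or with symptoms. Nor can it be said that the unexplained hepatocellular cases are lost, since those are the cases that the Hy's Law table is defined to show.

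**The Hy's Law table may be applied on laboratory values alone.** SAP 10.3.1 speaks of potential cases, and the working rule it spells out is that the bilirubin and transaminase elevations occur at the same visit. None of the forms it lists is named as recording causality. Protocol 11.1.1.3 also has potential cases reported before the search for a cause is finished. If the table is run on laboratory values only, the residual group would appear there. The written definition does include the alternative-explanation condition, however, and the SAP does not say how it will be applied.

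**Individual data survive elsewhere.** SAP 10.3.1 plans listings of subjects with liver-injury data, and protocol 11.6.1 requires all such events to be reported as adverse events. SAP 10.3 with Appendix 14.1.2 also gives counts for raised ALT, AST and bilirubin. This all stands, but those laboratory counts are set parameter by parameter, and none gives the joint count.

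**The cell may be a table-reading fault, or the shell may differ.** The text comes from a PDF, the blank ALP cells could be merged or lost cells, and the sponsor's standard shell to which the SAP refers is not among the documents. This calls for a check. It does not displace the printed text, which has five entries under five headings and a sentence naming ALP among the criteria.

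**Conclusion.** Wrong as written, minor. Row 1 of the SAP table does not match the protocol criterion it appears to represent, and SAP 3.9 does not record the difference as a deliberate change. As printed it captures 12 of 24 logical combinations meeting the protocol criterion, and 4 of 24 fall in no row of the table. No planned summary gives the number per arm meeting the criterion.

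These fractions describe the logic of the table, not patients. The documents give no incidence of such events and no randomized total after the early termination noted in the SAP. The protocol planned about 400 subjects outside China, and few events are likely at that size.

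The conclusion rests on three assumptions: that the ALP cell in row 1 is printed in the source as it appears here, that ALT and AST are joined by *or*, and that the other columns are joined by *and*. The statement about the residual group further assumes that the Hy's Law definition is applied literally.

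A reader might also infer that the SAP alters who must stop study drug. It does not: the stopping rule is in the protocol, and the SAP table only counts. No efficacy analysis is affected.

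**What to change.** First check the ALP cell of row 1 against the source table and the standard shell. If it stands as printed, reconcile row 1 with protocol 6.3.1 and Table 11-3:

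- Define the row as ALT *or* AST ≥3xULN and total bilirubin ≥2xULN at the same visit, regardless of ALP, and state the *or* for the whole table.
- Show ALP ≥2xULN and ALP <2xULN as two sub-rows, which keeps the information on possible biliary obstruction.
- State whether the alternative-explanation condition in the Hy's Law table is applied from recorded data or whether the table uses laboratory values only.

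If the ALP condition was intended, list it in SAP 3.9 with a reason and add a row for the protocol criterion.

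The cost is one row and a line or two of text in the SAP, and the matching change to the shell. ALP is already a planned laboratory parameter, so no new data are needed, and no clinical rule changes.
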